#### 7.4 Patient transfer and withdrawal

Follow-up of patients who stop treatment or transfer to another hospital will be continued through the individual study participating centres, unless the participant explicitly withdraws consent for follow-up.

#### 7.4.1 Patient Transfers

For patients moving from the area, every effort should be made for the patient to be followed-up at another participating centre and for this centre to take over responsibility for the patient.

The patient (or parent/legal representative) will have to sign a new consent form at the new site, and until this occurs, the patient remains the responsibility of the original centre. The Study Co-ordinating Centre should be notified in writing of patient transfers.

#### 7.4.2 Withdrawal from the study

Patients are free to withdraw consent at any time without providing a reason. Cessation of systemic therapy for whatever reason is, however, not a reason to withdraw from study follow up. Patients may also opt to remain in the study but withdraw from specific aspects such as not to provide further samples, complete further questionnaires, or be contactable.

A withdraw form will be sought from the patient where subject will be able to indicate specifics of withdrawing. If consent is withdrawn completely then the reasons for withdrawal of consent will be collected (if possible) and reported. Participants who wish to withdraw consent for the study will have anonymised data collected up to the point of that withdrawal of consent included in the analyses and long term follow up data linked, unless the patient explicitly states in the form that this is not their wish. The patient will not contribute further data to the study, and the Study Co-ordinating Centre should be informed in writing by the responsible physician and a withdrawal CRF should be completed. If instructed by the patient, the Study Co-ordinating Centre should notify laboratories that are in possession of samples that belong to patients who have withdrawn and request that their stored samples should be destroyed. The destruction of the samples will be adequately documented.

#### 7.5 Concomitant medications/treatments

A concomitant medication/treatment is any drug or substance administered between the baseline visit and the follow up visits, for atopic eczema or any other condition. All such medications should be reported to the investigator and recorded on the eCRF.

#### 7.5.1 Medications in addition to systemic atopic eczema medication

It is expected that all study participants will be on concomitant topical therapy for their atopic eczema, in particular regular emollients but also potentially (antiseptic) bath additives and mild-to-potent topical corticosteroids (TCS) of the patient's/local investigator's choice. Topical calcineurin inhibitors and oral antihistamines and antibiotics as well as rescue oral corticosteroids will be recorded.

Any medication required for any ongoing illness, birth contraception and any rescue medications will also be recorded both during the treatment and follow up period.

It is the responsibility of the local PIs to check potential drug interactions with the systemic medication the patient is on for their atopic eczema.

Pregnancy testing should follow local clinical practice and SOPs and is the responsibility of the local PI and study team.

#### 7.5.2 Medications precautions required

Advice on avoidance of live vaccines while on systemic immuno-suppressive therapy must be given, but is ultimately the responsibility of the local prescribing physician. All other advice/counselling provided to patients on any of the drugs prescribed should be in keeping with the SmPCs for each systemic medication.

## 7.6 Co-enrolment guidelines

Patients registered with A-STAR are not precluded from entering clinical trials. Where recruitment into another study occurs, it should be considered to be appropriate and without having any detrimental effect on the systemic medication. This should be recorded on the eCRF. The following procedure has been developed to deal with the various scenarios:

## Procedure for handling data on patients who are registered with A-STAR who enter into clinical trials i) If a patient registered with A-STAR enters into an un-blinded investigator sponsored clinical trial, the patient

data may be collected and processed in the usual way. The medication or dosing regimen may need to be added to the eCRF dropdown.

- ii) If a patient registered with A-STAR enters into an un-blinded clinical trial sponsored by a pharmaceutical company then subject to the consent of the pharmaceutical company the patient data may be collected and processed in the usual way. As A-STAR may have no formal contract with this pharmaceutical company, the relevant Principal Investigator would negotiate this with the pharmaceutical company and communicate the response to the Study Co-ordinating Centre.
- iii) If a patient registered with A-STAR enters into a blinded clinical trial, the data would be censored at the time of entry onto the clinical trial. After discontinuation of the RCT, the patient could be reinstated as long as they continue to agree participation in A-STAR (to be documented in medical notes). If the blinding code has been opened, A-STAR would like to collect the data relevant to that period as long as permission has been given by the trial sponsor. The responsibility to obtain this permission would lie with the Principal Investigator as A-STAR may have no formal agreement with this pharmaceutical company.

## 7.7 Recall of patients

In cases where genetic or other biomarkers of disease and/or treatment outcomes require further phenotypic and biological validation we may wish to recall individual patients for collection of additional biological samples. This recall is entirely voluntary as stated in the Informed Consent Form. If it is necessary to contact the patient in the future a member of the study team will contact the subject by phone or approach them at their next clinic visit and ask if they are still willing to provide additional samples.

#### 8 ASSESSMENTS AND PROCEDURES

## 8.1 Procedures for assessing effectiveness

Effectiveness of the study medications will be assessed throughout the period of the study using objective measures and patient-reported outcomes.

The primary outcome measure for the study is the change in atopic eczema severity from baseline, using the EASI score, conducted by a trained member of the study team. We will also assess severity with the IGA and POEM scores at baseline and all follow up visits, and ACT (for patients ≥12 years old who have a doctor-diagnosis of asthma).

## 8.2 Procedures for adverse events/pharmacovigilance

The following safety bloods and investigations will be performed to assess treatment safety and collect pharmacovigilance data:

- a. Safety blood profiles (full blood count, renal function, and liver function) will be taken at screening/baseline, week 4 and week 16, and at every follow up visit thereafter while on treatment. Blood samples may be done at the local GP practice as long as the results can be provided to the treating centre. Other safety bloods may be done, in keeping with local clinical practice (e.g. IgE, hepatitis B and C as well as HIV screen). If it is not possible to obtain a safety blood sample (e.g. insufficient sample, participant refusal) at their visit, the assessments/procedures can be carried out as normal and the patient can continue in the study. However, the Investigator needs to assess whether it is safe for the patient to continue with their systemic drug treatment.
- b. BP will be taken at baseline, 4, 16 weeks and then at every follow up visit while on systemic treatment, where change in BP is anticipated (e.g. ciclosporin).
- c. Physical examination will be carried out at each visit.
- d. A careful history of all potential adverse events since the last clinic visits will be taken and entered into the eCRF. This will cover in particular but not exclusively the following:
  - Specific prompt for serious infection (e.g. pneumonia, septicaemia, bone/joint infection, opportunistic infection, and soft tissue/skin infection, TB, respiratory (non-infectious), cardiac disorders, CNS disorders, haematological events, malignancy (skin cancer and non-cutaneous cancer), pregnancy, and death
  - Was patient on immune-modulatory/biologic treatment therapy at the time of onset of event?
  - Date of last treatment/injection
  - Did this result in death, hospitalisation or prolongation, loss of function, significant disability, congenital malformation or was in any other way life threatening?
  - Do you believe that there is a reasonable possibility that this event was related to the patient's immune-modulatory/biologic treatment therapy?

The eCRF will remind the user that a yellow card /HPRA notification must be filled if applicable.

Data on adverse events, including severity, seriousness, and expectedness as part of pharmacovigilance will be recorded at each follow-up visit and entered into the eCRF. Requirements for pharmacovigilance reporting is detailed fully in Section 10 (Pharmacovigilance).

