tape stripping for cutaneous cytokine profiles, and skin swab samples for microbiome work (optional).
Descriptive and exploratory data analyses will be conducted on a 6-monthly basis. All participating centres will receive a summary report of all patients as well as their own.

Version and date of protocol amendments:	V2.0 (26-FEB-2019) V3.0 (09-AUG-2021) V4.0 (01-JUL-2022) V4.1 (12-MAR-2024) V5.0 (08-APR-2025)
---	--

	V1	V1b	V2	V3	V4	V5	V6	
Study visits and assessments	Baseline	Day	4 weeks	16 weeks	6 months	9 months	12 months	Baseline 2,
		1 h					**	3, 4 etc.
	(-28 days)		(+/- 2 wk i )	(+/-4 wk j )	(+/-4 wk)	(+/-4 wk)	and subseq.	(where
							Visits	applicable)
							(+/-4 wk)	***
Informed consent	Х							
Inclusion/exclusion criteria	Х							
Demographics	Х							Х
Personal/family history	Х							
Smoking and alcohol consumption	Х		Х	Х	Х	Х	Х	Х
Atopic Eczema and treatment history	Х		Х	Х	Х	Х	Х	Х
Co-morbidities (including immediate	V		V	V	V	V	V	V
and delayed allergies)	Х		Х	Х	Х	Х	Х	Х
Concomitant medication	Х		Х	Х	Х	Х	Х	Х
Physical examination a	Х		Х	Х	Х	Х	Х	Х
Blood pressure (if applicable)	Х		Х	Х	Х	Х	Х	Х
Treatment (prescribed)	Х		Х	Х	Х	Х	Х	Х
Adverse events			Х	Х	Х	Х	Х	Х
Safety bloods b	Х		Х	Х	Х	Х	Х	Х
EASI, EASI-50, EASI-75	Х		Х	Х	Х	Х	Х	Х
IGA	Х		Х	Х	Х	Х	Х	Х
POEM	Х		Х	Х	Х	Х	Х	Х
Itch severity (numerical rating score)	Х		Х	Х	Х	Х	Х	Х
CDLQI/DLQI/IDQOL c	Х		Х	Х	Х	Х	Х	Х
EQ-5D-5L (adults) EQ-5D-Y (4-15 years old) c	Х		х	Х	х	х	Х	х
ACT c,d	Х			Х			Х	Х
RECAP c	X		Х	X	Х	Х	X	X
Collection of blood for FLG mutation and other genetic analysis (optional) e	х							
Collection and storage of blood samples for mechanistic studies, drug metabolite and trough level analyses (optional) f	Xg		Х	Х			х	х
Skin biopsies (optional, ≥16 years) f	Χg		х	х				
Skin swab samples (optional) f	Xg		Х	Х				
Tape stripping (optional) f	Χg		Х	Х				
Systemic immuno-modulatory therapy start	Λ-	Xh	^	^				
** Follow up will be six-monthly whether	r tha nationts	252.00.4	or off of system	mia tharanu tr	ootmont.	l .	I	

\*\* Follow up will be six-monthly whether the patients are on or off of systemic therapy treatment.

- a Includes height at baseline and weight at all timepoints. For minors, height at all timepoints.

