#### **6 STUDY POPULATION**

#### 6.1 Inclusion Criteria

- 1. Paediatric and adult patients with atopic eczema who due to the severity of their disease and/or impact on quality of life are commencing on or switching to another systemic immuno-modulatory agent (e.g. CsA, AZA, MTX or biologic treatments), or who initiated their treatment within the last four weeks and have all required pre-treatment outcomes available.
- 2. Written informed consent for study participation obtained from the patient or parents / legal guardian, with assent as appropriate by the patient, depending on the level of understanding.
- 3. Participants consent to participate in long-term follow up and access to all medical records, including hospital admission records and linkage to data held by NHS bodies or other national providers of healthcare data.
- 4. Diagnosis of atopic eczema in keeping with the UK diagnostic criteria.
- 5. Willingness to comply with all study requirements.
- 6. Competent use of English language, according to patient's age (capable of understanding patient questionnaires).

There is no upper or lower age limit for participation. The decision to start systemic therapy or switch to another systemic agent will be the result of the treating dermatology consultant's decision, following discussion with the patient/parent/legal guardian, without using a pre-specified severity score cut off. It is the treating physician's responsibility to ensure that patients are suitable for the therapy, and that any standard of care treatment or assessments are provided alongside participation in the study as per local requirements.

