#### 7.2 Baseline visit

The baseline visit of potentially eligible participants will take place following written informed consent to participate. Informed consent can also be taken prior to the baseline visit, and patients will have been provided with verbal and written study information beforehand, providing adequate time to consider the implication of taking part. A copy of the consent and assent forms should be kept in the ISF at the participating site, and the consent process documented in the medical notes. Data from clinical assessments undertaken as part of routine care prior to obtaining consent can be used (i.e. safety blood) for assessing eligibility.

The visit will include:

- a. written informed consent will be obtained from the patient or parent/legal guardian
- b. full medical history, including family history and personal history of co-morbidities (including delayed and immediate allergies), atopic eczema diagnosis and treatment history

- c. alcohol and smoking consumption
- d. assessment of eligibility criteria
- e. review of concomitant medication
- f. physical examination; including clinical phenotyping and eczema severity assessments (can be done by all team members who have completed the relevant training (see A-STAR study website under 'Training Resources') and who the local PI deems adequately experienced to conduct these assessments)
- g. blood pressure at the local investigator's discretion
- h. height and weight
- i. safety bloods. To include full blood count, renal and liver profile, total IgE (if part of routine practice), as well as virology (Hep B, Hep C and HIV) as per local practice.
- j. collection of demographic data
- k. completion of EASI, EASI-50, EASI-75 and IGA and POEM, itch severity (NRS), IDQOL/CDLQI/DLQI, EQ-5D-5L (adults)/EQ-5D-Y (4-16 years' old), RECAP
- I. completion of ACT in patients with diagnosed asthma of ≥ 12 years' old
- m. optional: collection of blood for genetic analysis
- n. optional: collection and storage of bloods samples for mechanistic studies, skin biopsies (≥16 years of age), and tape stripping for cutaneous cytokine analyses as well as sample collection for skin microbiome/metabolite work, using standardised operation procedures across all study participating centres that have the expertise and facilities to take part on this module.

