## 7.3 Follow up visits

Follow up visits will occur at 4 weeks after the start of systemic immuno-modulatory therapy, 16 weeks and three-monthly thereafter whilst on systemic therapy up to Visit 6 (12 months). Then follow up visits will be every six months (for example: Visit 7 will be at 18 months, Visit 8 will be at 24 months and so on). Once treatment has been stopped, follow ups are also done six-monthly.

If a patient is recruited within the first 2 weeks after treatment initiation, visit 2 will happen at week 4 (±2 weeks), as per usual schedule of events. In situations when patient recruitment occurs 3-4 weeks after treatment initiation, visit 2 assessments will be conducted on the day of recruitment.

Follow up visit procedures:

a. Confirm informed consent status.

- b. Review of co-morbidities and concomitant medication.
- c. Review of systemic therapy (any changes since last visit/current dose) and disease control (number of controlled weeks).
- d. If treatment has been switched: reasons for switching, and outcomes in patients at the point at which the subsequent treatment is initiated.
- e. Reasons if discontinuing (lack of effectiveness, adverse events, patient preference, disease remission, other).
- f. Smoking and alcohol consumption.
- g. Review of adverse events experienced since the previous visit.
- h. Any A&E, hospital, GP or healthcare skin-related visits, and whether due to disease exacerbations, including skin infection.
- i. Days lost from usual activities due to skin disease (e.g. school, work).
- j. Any further phototherapy (TL01, PUVA or other; number of doses).
- k. Physical exam (at the discretion of the treating physician and with their oversight), including weight, and BP.
- I. Safety blood samples are recommended at all study visits.
- m. EASI, -IGA, POEM, itch severity (NRS), IDQOL/CDLQI/DLQI, EQ-5D-5L (adults)/EQ-5D-Y (4-16 years' old), and RECAP.
- n. Completion of ACT in subjects with diagnosed asthma of ≥ 12 years' old\*.
- o. Optional: collection of blood samples, skin biopsies (≥16 years of age), and skin tape strips for mechanistic work and collection of skin microbiome/metabolite samples, using standardised operation procedures across all study participating centres that have the expertise and facilities to take part on this module.\*\*
- \*ACT only done at 16 weeks and 12 months and then every six months.
- \*\*Only done at 4 and 16 weeks, as well as, one year into treatment.

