#### 7.3.1 Unscheduled visits

In some circumstances a patient may need to return to clinic outside of the suggested follow up visits, for instance due to a disease flare. Patient might also be admitted for severe disease exacerbations. If that is the case, data should be recorded on the eCRF. All data will be collected as if a routine follow up visit but with the addition of:

- Reason for return
- Adverse events
- Safety bloods (only collected if part of the reason for the unscheduled visit)
- Concomitant medications
- Blood pressure (only if part of the reason for the unscheduled visit)
- Outcome of the visit
- Severity assessment (EASI, EASI-50, EASI-75 & IGA, POEM and EQ-5D-5L (adults)/EQ-5D-Y (children)

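### Scheduled blood pressure measurement depends on the drug's expected effect, so asymptomatic raised blood pressure may be detected unequally between drugs

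*Protocol*

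**What the plan says.** The protocol gives BP instructions for scheduled visits in several places.

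- **Section 8.2(b)** lists baseline, week 4 and week 16, and continues "at every follow up visit while on systemic treatment, where change in BP is anticipated (e.g. ciclosporin".
- **Section 8.2(c)**, the next item, states "Physical examination will be carried out at each visit".
- **Section 7.2(g)**, for the baseline visit, has "blood pressure at the local investigator's discretion".
- **Section 7.3(k)**, for follow-up visits, has "Physical exam (at the discretion of the treating physician and with their oversight), including weight, and BP".
- **The schedule table in Section 2** marks BP at V1 to V6 and at any new baseline, in a row labelled "Blood pressure (if applicable".

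Three other provisions determine what happens to the readings. Section 10.2.1 counts a physiological or examination abnormality as an adverse event when it calls for further investigation or clinical intervention. Section 9.2 makes the comparison of adverse event profiles across treatment groups the fourth secondary endpoint. Section 9.4 compares event rates between groups by regression, with multivariable adjustment and possibly propensity score matching, both directed at confounding.

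**The concern.** Raised BP without symptoms becomes an event only if someone takes a reading. If the plan directs readings towards drugs already expected to raise BP, an excess of such events on ciclosporin would partly reflect how often BP was looked for. A rise on a drug not expected to affect BP could be missed. The second problem matters for the newer biologics and small molecules that the register admits, because a rule based on expectation is weakest at finding the unexpected.

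The planned adjustment does not help. Covariates and propensity scores balance who receives which drug, not who is measured. Readings that were never taken cannot be restored at the analysis stage, so this has to be settled in the protocol's procedures.

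**Working it through.** The protocol states no figure for BP measurement, so there is none to reproduce. The check compares the instructions and then counts the time points at which each reading of them secures a measurement.

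**Step 1. Does any instruction secure BP equally across drugs?**

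- In 8.2(b) the condition may govern the whole list of visits (broad reading) or only those after week 16 (narrow reading). Both depend on the drug.
- 7.2(g) leaves baseline BP to discretion on every drug, ciclosporin included.
- 7.3(k) puts BP inside an examination that is itself discretionary.
- 8.2(c) removes that discretion. If the examination in 8.2(c) is the one described in 7.3(k), BP is due at every follow-up on every drug. That reading is possible, but it leaves the condition in 8.2(b) with nothing to do at follow-up.
- The label in the schedule table fits all of these readings and decides between none of them.

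Equal measurement is therefore not secured. One reading gives it at follow-up, and none gives it at baseline once 7.2(g) is applied.

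**Step 2. Count the first-year time points.** The schedule has V1 to V6: one baseline and 6 − 1 = 5 follow-ups (weeks 4 and 16, months 6, 9 and 12).

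| Reading | Drug expected to affect BP | Any other drug |
|---|---|---|
| 8.2(b) alone, broad | 6 of 6 | 0 of 6 |
| 8.2(b) alone, narrow | 6 of 6 | 3 of 6 |
| 8.2(b), broad, follow-ups only | 5 of 5 | 0 of 5 |
| 8.2(b), narrow, follow-ups only | 5 of 5 | 3 − 1 = 2 of 5 |
| 7.3(k) with 8.2(c) as mandatory, follow-ups only | 5 of 5 | 5 of 5 |

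The follow-up rows are the safer ones, because 7.2(g) makes baseline BP discretionary for everyone. The first-year difference is 5, 3 or 0 follow-up visits, depending on the reading. These are visits that the wording guarantees, not visits at which BP is actually taken.

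**Step 3. Follow a reading into the comparison.** A reading is taken (8.2(b)), is found raised, needs investigation or intervention (10.2.1), is counted per person-time (9.4) and is compared between drugs (9.2, 9.4). The first link depends on the drug, and no later step adjusts for that.

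**Step 4. Can the bias be sized?** Not from the protocol, which gives no measurement share and no rate of raised BP. The form of the bias is

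apparent rate ratio = true rate ratio × (share detected on drug A ÷ share detected on drug B).

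With a true ratio of 1, and purely assumed detection of 100% on A against 80%, 50% or 30% on B, the apparent ratio is 1 ÷ 0.8 = 1.25, 1 ÷ 0.5 = 2.0 or 1 ÷ 0.3 = 3.3. This shows the mechanism only and is not evidence about this register.

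**The case against.** The strongest reply is that this is deliberate. The register is observational and adds no study-specific intervention, so BP taken where clinically indicated fits the design. Drug-tailored monitoring also appears elsewhere: a note to the schedule allows an extra week 1 blood sample on methotrexate. The reach is narrow too. BP defines no endpoint, hypertension is not among the named safety concerns, and diagnosed or treated cases can still enter through adverse event history, comorbidity and medication review, and data linkage. The counts describe wording, not practice.

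Most of this stands, and it limits the point without removing it. A routine-care rationale explains the discretion, but the protocol still plans a formal comparison of event rates between drugs.

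A reader might infer four stronger claims that the document does not support.

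- **Unscheduled visits.** Section 7.3.1 has "Blood pressure (only if part of the reason for the unscheduled visit". That rule applies to every drug alike and puts the same condition on safety bloods, so it is no drug-specific detection rule.
- **Safety bloods as a compulsory model.** Section 8.2(a) sets bloods "and at every follow up visit thereafter while on treatment" without naming a drug, but Section 7.3 and the schedule notes only recommend them. They show that a rule can be written without a drug condition, not that one is enforced.
- **A gap widening over ten years of treatment.** The only drug named in 8.2(b) is ciclosporin, and Section 3.1 says that renal toxicity limits its long-term use. Ten years on it is not a realistic comparator.
- **Removing BP events from the fourth secondary endpoint.** That would drop an effect the protocol itself anticipates. It would also require sorting past readings by the reason they were taken, which the protocol makes no provision to record at scheduled visits.

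**Conclusion.** The point holds in a limited form. Section 8.2(b) makes scheduled BP measurement depend on the drug, at all visits or after week 16, and no other instruction clearly restores equality. Asymptomatic raised BP may therefore be detected more often on ciclosporin than on other drugs, and the planned adjustment would not correct this. The first-year difference in guaranteed follow-up readings is 5 or 3 visits on the two readings of 8.2(b). It is 0 if 7.3(k) and 8.2(c) are together taken as mandatory.

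The conclusion assumes that sites follow the wording. If they already measure BP on every drug, there is little or no bias; the protocol does not say. The size cannot be derived. The effect is confined to BP events found by measurement: the EASI endpoint is unaffected, and diagnosed or treated cases largely so. It is a worthwhile repair to the safety comparison, not a reason to doubt that comparison as a whole.

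**What to change.** Align the schedule table and Sections 7.2(g), 7.3(k) and 8.2(b) to one rule that does not depend on the drug: BP is recorded, or marked not done, at baseline and at each scheduled in-person visit while on systemic treatment. State an age exception for young children, since Section 6.1 says "There is no upper or lower age limit for participation". Mark remote visits, which Section 12.1 allows in exceptional circumstances, as not done.

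For any between-drug comparison of BP-related events, report the share of visits with BP measured by drug, including visits already made under the current wording, and interpret the comparison in that light. Keep these events in the fourth secondary endpoint.

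The cost is an amendment to four places and one brief added reading for patients on drugs with no expected BP effect. These visits already carry a BP row in the schedule and an examination under 8.2(c). Readings not taken so far stay missing, which is why the measured share needs to be reported.
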